9.5.1 Outcome Definitions

E. coli = The proportion of children participating in the antimicrobial resistance substudy whose stool was submitted for antimicrobial resistance testing, among whom azithromycin resistant *E. coli* was detected in the day 90 (main analysis) and day 180 stool specimens.

S. pneumoniae = The proportion of children participating in the antimicrobial resistance substudy whose stool was submitted for antimicrobial resistance testing among whom azithromycin resistant *S. pneumoniae* was detected at day 90 (main analysis) and day 180 nasopharyngeal swab specimen.

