9.5 Analysis of Secondary Objective 8 – Antibiotic resistance in enrolled participants

To compare prevalence of azithromycin resistant *E.coli* and azithromycin resistant *S. pneumoniae* respectively in stool and nasopharyngeal swabs submitted for antimicrobial resistance testing at D90 and D180 among a random subsample of enrolled participants, by trial allocation arm.

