9.5.2 Analysis

Four non-superiority hypothesis tests (2 samples and 2 timepoints) will be conducted to test whether the difference in prevalence of resistance at day 90 and day 180 in children assigned

to the azithromycin (R_{AZM}) and placebo ($R_{placebo}$) group exceeds a margin of 10% (one sided test).

E. coli Day 90

H_0 : $R_{AZM} - R_{placebo} > 10\%$
 H_1 : $R_{AZM} - R_{placebo} \leq 10\%$

E. coli Day 180

H_0 : $R_{AZM} - R_{placebo} > 10\%$
 H_1 : $R_{AZM} - R_{placebo} \leq 10\%$

S. pneumoniae Day 90

H_0 : $R_{AZM} - R_{placebo} > 10\%$
 H_1 : $R_{AZM} - R_{placebo} \leq 10\%$

S. pneumoniae Day 180

H_0 : $R_{AZM} - R_{placebo} > 10\%$
 H_1 : $R_{AZM} - R_{placebo} \leq 10\%$

Justification for the NI margin of 10%: this margin has been chosen based on clinical acceptability among infectious disease experts. Also, consultation with investigators in other trials of azithromycin accept a 10% (absolute difference) NI margin as reasonable. The non-inferiority hypothesis will be tested using the continuity corrected χ^2 test as suggested by Dunnett and Gent, Biometrics 1977.

In primary analysis, the prevalence denominator will be all children enrolled in the AMR sub-study whose stool was submitted for antimicrobial sensitivity testing (irrespective of whether the bacteria was isolated). Those children who were enrolled in the AMR study, who provided a sample, but whose sample could not be subject to an antibiotic sensitivity test because of external circumstances (COVID-19 related lockdowns of the lab), will be excluded from the denominator. At sites, that have experienced a lockdown, random distribution of selection of specimens for testing will be difficult to confirm, though examination for systematic bias (eg by date range) will be undertaken. If bias is suggested in sites that have not completed testing, these sites will be excluded from hypothesis testing. But other remaining sites will be included in non-inferiority test as outlined above.

In secondary analysis, the prevalence denominator will be defined as those children in whom the respective bacteria was isolated and tested (i.e. azithromycin resistance in *E. coli* as a proportion of *E. coli* isolates, and likewise for *S. pneumoniae*). Sites that have not completed testing as outlined above, will be dealt with as outlined above.

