9.6.1 Outcome Definitions

E. coli = The proportion of child contacts participating in the antimicrobial resistance substudy whose stool was submitted for antimicrobial resistance testing among whom azithromycin resistant *E. coli* was detected in the day 90 (main analysis) and day 180 stool specimen.

S. pneumoniae = The proportion of child contacts participating in the antimicrobial resistance substudy whose stool was submitted for antimicrobial resistance testing among whom azithromycin resistant *S. pneumoniae* was detected at day 90 (main analysis) and day 180 nasopharyngeal swab specimen.

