9.6.2 Analysis

Four non-inferiority hypothesis tests (2 samples and 2 timepoints) will be conducted to test whether the difference in prevalence of resistance in children assigned to the azithromycin and placebo group exceeds 10% (one sided test).

E.coli Day 90

H₀: $R_{AZM} - R_{placebo} > 10\%$
H₁: $R_{AZM} - R_{placebo} \leq 10\%$

E.coli Day 180

H₀: $R_{AZM} - R_{placebo} > 10\%$
H₁: $R_{AZM} - R_{placebo} \leq 10\%$

S. pneumoniae Day 90

H₀: $R_{AZM} - R_{placebo} > 10\%$
H₁: $R_{AZM} - R_{placebo} \leq 10\%$

S. pneumoniae Day 180

H₀: $R_{AZM} - R_{placebo} > 10\%$
H₁: $R_{AZM} - R_{placebo} \leq 10\%$

Although this analysis is predefined, we anticipate low power for this analysis. Justification for the NI margin of 10%: this margin has been chosen based on clinical acceptability among

infectious disease experts. Also, consultation with investigators in other trials of azithromycin accept a 10% (absolute difference) NI margin as reasonable. The non-inferiority hypothesis will be tested using the continuity corrected χ^2 test as suggested by Dunnett and Gent, Biometrics 1977. Since all participants will not provide a contact for sampling (stool or swab), an examination for systematic bias among the contacts who provided samples that were submitted for testing (eg by date range, site) will be undertaken. Any apparent bias will be described, and potentially adjusted for using a modeling framework.

In the primary analysis, the denominator of these prevalence estimates will be all child contacts enrolled in the AMR sub-study whose stool was submitted for antimicrobial sensitivity testing (irrespective of whether the bacteria was isolated). Treatment of sites affected by COVID-19 lockdowns will be as outlined in Section 9.5.2.

In secondary analysis, the prevalence denominator will be defined as those contacts in whom the respective bacteria was isolated and tested (i.e. azithromycin resistance in *E. coli* as a proportion of *E. coli* isolates, and likewise for *S. pneumoniae*). Sites that have not completed testing as outlined above, will be dealt with as outlined in Section 9.5.2.

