* from adjusted generalized linear mixed model

RR = Risk Ratio; CI = confidence interval

Table 5

	Baseline	Placebo group			Treated group		
		D90	D180	Adjusted p value	D90	D180	Adjusted p value
E. Coli -AZM resistance (mean, 95% CI) in participants							
By stool sample							
By isolates tested							
S. Pneumoniae - AZM resistance (mean, 95% CI) in participants							
By stool sample							
By isolates tested							
E. Coli -AZM resistance (mean, 95% CI) in community contacts							
By stool sample	NA						
By isolates tested	NA						
S. Pneumoniae - AZM resistance (mean, 95% CI) in community contacts							
By stool sample	NA						
By isolates tested	NA						

Table 6. Other reportable outcomes by trial arm

Outcome	Placebo	Azithromycin
Dosing adherence	n/N (%)	n/N (%)
Protocol deviations	n/N (%)	n/N (%)

Table 6. Baseline characteristics and other reportable outcomes by country of enrolment

Variable	Bangladesh	India	Pakistan	Mali	Tanzania
Number of participants	xxx	xxx	xxx	xxx	xxx
Mean (SD) age, months	xx.x (xx.x)				
Proportion male, %	xx.X%	xx.X%	xx.X%	xx.X%	xx.X%
Mean (SD) weight, kg	xx.x (xx.x)				
Mean (SD) length, cm	xx.x (xx.x)				
Mean (SD) MUAC, cm	xx.x (xx.x)				
Mean (SD) LAZ, z-score units	xx.x (xx.x)				
Mean (SD) WLZ, z-score units	xx.xx (xx.xx)				
Prevalence of moderate stunting (-3.0<LAZ≤-2.0), %	xx.xx (xx.xx)				
Prevalence of severe stunting (LAZ≤-3.0), %	xx.xx (xx.xx)				
Prevalence of moderate wasting (-3.0<WLZ≤-2.0), %	xx.xx (xx.xx)				
Prevalence of some or severe dehydration, %	xx.xx (xx.xx)				
Mean (SD) maternal age, years	xx.x (xx.x)				
Mean (SD) maternal height, cm	xx.x (xx.x)				
Mean (SD) maternal weight, kg	xx.x (xx.x)				
Mean (SD) maternal BMI, kg / m ²	xx.x (xx.x)				
Mean (SD) maternal MUAC, cm	xx.x (xx.x)				
Mean (SD) maternal education, years	xx.x (xx.x)				
Mean (SD) number of children below 5 years of age in the household	xx.x (xx.x)				
Dosing adherence to protocol	n (%)				
Protocol deviations	n (%)				

SD = standard deviation; MUAC = mid-upper arm circumference; LAZ = length-for-age Z-score; WLZ = weight-for-length Z-score; BMI = body mass index

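### The primary S. pneumoniae resistance analysis uses stool submission as its denominator, although the organism is read from the nasopharyngeal swab

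*SAP*

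**What the plan says.** The opening paragraph of SAP 9.5 matches each organism to its own specimen: E. coli and S. pneumoniae are assessed "respectively in stool and nasopharyngeal swabs submitted for antimicrobial resistance testing at D90 and D180". The opening of 9.6 does the same for contacts. Protocol 6.5 agrees: stool is plated for E. coli, and swabs go into their own transport medium and are plated for S. pneumoniae.

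The operative text says something else:

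- **SAP 9.5.1, participants.** The E. coli proportion is taken among children "whose stool was submitted for antimicrobial resistance testing, among whom azithromycin resistant" bacteria were found in stool. The S. pneumoniae proportion repeats the stool condition (the words differ only by a comma), but its result "was detected at day 90 (main analysis) and day 180 nasopharyngeal swab specimen".
- **SAP 9.5.2, primary analysis.** One rule serves both organisms: "the prevalence denominator will be all children enrolled in the AMR sub-study whose stool was submitted for antimicrobial sensitivity testing", whether or not the organism grew.
- **SAP 9.6.1 and 9.6.2, contacts.** The definitions use contacts "whose stool was submitted for antimicrobial resistance testing among whom azithromycin resistant" organisms were found, and the analysis uses "all child contacts enrolled in the AMR sub-study whose stool was submitted for antimicrobial sensitivity testing".
- **SAP Table 5.** Under "S. Pneumoniae - AZM resistance (mean, 95% CI) in participants" and the matching contact heading, the first row is labelled as per stool sample.
- **SAP 9.5.2, COVID-19 exclusion.** It removes children who gave a sample "but whose sample could not be subject to an antibiotic sensitivity test because of external circumstances", without naming the specimen.

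No text gives a swab-based denominator for the primary analysis or limits the stool rule to E. coli. Only the secondary analysis, which counts isolates of the respective organism, is specific to the organism.

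**The concern.** The numerator comes from one specimen and the denominator from another. Two errors follow if the text is applied as written. A child whose stool was submitted but who has no swab result cannot show resistant S. pneumoniae, so that child enters as non-resistant. A child with a known swab result but no stool is left out.

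The tests concerned are one-sided non-inferiority tests of whether resistance under azithromycin is within 10 percentage points of placebo. Children counted as non-resistant by default pull both prevalences towards zero and, with equal swab coverage in the two arms, shrink the gap. That favours the reassuring conclusion. The Protocol's Background section wants resistance documented so that benefit and risk can be weighed before any policy change, so this secondary result has weight. SAP section 11 also rules out parallel analyses of the same question, so the choice between two possible analysis sets has to be settled in the text.

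**Working it through.** **The plan's own figure.** Protocol 10.3 asks for 119 isolates per arm: 20% against 40%, 90% power, alpha 0.05. Without continuity correction, n' = [1.96·√(2·0.3·0.7) + 1.2816·√(0.2·0.8 + 0.4·0.6)]² / 0.2² = 108.2, rounded up to 109. With it, n = (n'/4)·[1 + √(1 + 4/(0.2·n'))]² = 118.0, rounded up to 119. The Table 2 losses give 345 × 0.9 × 0.8 × 0.8 × 0.67 × 0.9 = 119.8. The figure reproduces (two-sided). It counts isolates, so the denominator question does not change it.

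**Effect of the stool denominator.** Let f be the share of stool-submitting children who also have a swab result, and pP and pA the true per-swab prevalences of resistant S. pneumoniae. The documents give no value for f; everything below is conditional on it.

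Observed gap = fA·pA − fP·pP. With equal f this is f × true gap, so a true gap of 10/f points reads as exactly 10:

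| f, both arms | True 10 points reads as | True gap that reads as 10 |
|---|---|---|
| 0.95 | 9.5 | 10.5 |
| 0.90 | 9.0 | 11.1 |
| 0.80 | 8.0 | 12.5 |
| 0.70 | 7.0 | 14.3 |

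With unequal coverage the direction depends on the arm. Take a true 20% against 30%:

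- fP = 0.80, fA = 0.90: 0.27 − 0.16 = 11.0 points.
- fP = 0.90, fA = 0.80: 0.24 − 0.18 = 6.0 points.

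**Chance of wrongly concluding within 10 points when the true gap is exactly 10.** Inputs:

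- n = 1,600 × 0.90 × 0.80 / 2 = 576 per arm: the lower planned sub-study size less Table 2's 10% loss and 20% refusal. Recruitment stopped early, so this is a planning figure.
- Placebo prevalence per swab: 0.20 × 0.67 = 13.4% (Protocol 10.3 resistance times Table 2 colonisation), or 20%.
- One-sided alpha 0.05. This is an assumption: SAP 9.5.2 gives no level, and Protocol section 10 sets 0.05 without addressing one-sided tests.
- The continuity-corrected chi-square test named in 9.5.2, by simulation.

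| f | Placebo 13.4% | Placebo 20% |
|---|---|---|
| 1.00 | 4.8% | 4.6% |
| 0.95 | 7.5% | 6.9% |
| 0.90 | 11.6% | 10.2% |
| 0.80 | 24.9% | 20.5% |

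A hand check uses the unpooled normal approximation, Φ[(0.10 − 0.10f)/SE − 1.645]. At f = 0.90 and pP = 13.4% the observed proportions are 0.1206 and 0.2106, SE = √[(0.1206·0.8794 + 0.2106·0.7894)/576] = 0.0217, and the result is 11.8%.

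**Sensitivity to n and alpha (same approximation, f = 0.90, placebo 13.4%).** At one-sided 0.025 with 576 per arm, the rate goes from 2.5% to 6.7%. With 248 per arm (Table 2's number per region after refusal), it goes from 5.0% to 9.0% at one-sided 0.05 and from 2.5% to 4.9% at 0.025.

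**The case against.** The intent can be recovered. The openings of 9.5 and 9.6 pair organism with specimen, and the outcome sentence itself names the swab. A sensible analyst might use swabs without being told.

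The inflated error rates all need children with stool but no swab. The better-supported case in the documents is the reverse. Protocol 6.5 allows the rectal-swab fallback for stool only at the clinic and with the caregiver's permission, while Protocol 6.2 lets the day 90 visit take place at home. Dropping swab-only children costs precision but does not dilute the gap unless the loss is informative. With n cut from 576 to 518 or 461 per arm (10% or 20% dropped), the error rate stays at about 4.3-4.4%.

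Table 2 treats refusal as one event and 576 already has it removed, so f = 0.80 assumes a further swab-specific loss. Random sub-study selection stratified by arm, together with blinding, makes unequal coverage unlikely. The COVID-19 exclusion can be read to cover swabs left untested by lockdowns, and the isolate-based analysis is untouched.

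Most of this stands as a limit on size. Low f is unsupported, and 20-25% is the far end of the range. Stool without a swab is still possible: the Bangladesh, India, Kenya, Malawi and Tanzania site plans describe follow-up specimens as stool only, although Protocol 4.3 covers nasopharyngeal samples at consent. The COVID-19 exclusion does not reach a swab that was refused or never taken. The recoverable intent does not remove the conflict, because the rule that builds the denominator says stool in every place where it is stated.

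**Conclusion.** The concern holds. The SAP's stated denominator for the primary S. pneumoniae analysis is wrong as written, for participants and for contacts, and it conflicts with the SAP's own pairing of organism and specimen. The analysis belongs to a secondary objective, not to a primary trial endpoint.

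How much this moves the result cannot be known from the documents. With equal swab coverage in both arms the gap shrinks in proportion to f, which leans towards concluding that resistance is within the margin. At f = 0.95 to 0.90 the wrong-conclusion rate is roughly 7% to 12% instead of about 5%, given 576 per arm, one-sided 0.05 and placebo prevalence of 13.4% to 20%. It is lower with fewer children or at a stricter alpha. Unequal coverage could push the gap either way. If almost all children supplied both specimens, the two denominators coincide and nothing changes.

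**What to change.** In SAP 9.5.1 and 9.5.2, define the primary S. pneumoniae denominator as children whose nasopharyngeal swab was submitted for testing at that visit. Make the same change for contacts in 9.6.1 and 9.6.2. Keep stool submission for E. coli only. State that the COVID-19 exclusion works by specimen type, so that an untested swab removes a child from the S. pneumoniae analysis alone. Relabel the S. pneumoniae rows of Table 5 as per swab sample. Report by arm and visit how many children gave stool only, swab only or both, so that a reader can see whether the choice mattered.

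The cost is a few words in four sections, a table label and one short tabulation. It must be known which swabs were submitted at each visit; the documents do not say how that is recorded.

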9.5.2 Analysis

Four non-superiority hypothesis tests (2 samples and 2 timepoints) will be conducted to test whether the difference in prevalence of resistance at day 90 and day 180 in children assigned

to the azithromycin (R_{AZM}) and placebo ($R_{placebo}$) group exceeds a margin of 10% (one sided test).

E. coli Day 90

H_0 : $R_{AZM} - R_{placebo} > 10\%$
 H_1 : $R_{AZM} - R_{placebo} \leq 10\%$

E. coli Day 180

H_0 : $R_{AZM} - R_{placebo} > 10\%$
 H_1 : $R_{AZM} - R_{placebo} \leq 10\%$

S. pneumoniae Day 90

H_0 : $R_{AZM} - R_{placebo} > 10\%$
 H_1 : $R_{AZM} - R_{placebo} \leq 10\%$

S. pneumoniae Day 180

H_0 : $R_{AZM} - R_{placebo} > 10\%$
 H_1 : $R_{AZM} - R_{placebo} \leq 10\%$

Justification for the NI margin of 10%: this margin has been chosen based on clinical acceptability among infectious disease experts. Also, consultation with investigators in other trials of azithromycin accept a 10% (absolute difference) NI margin as reasonable. The non-inferiority hypothesis will be tested using the continuity corrected χ^2 test as suggested by Dunnett and Gent, Biometrics 1977.

In primary analysis, the prevalence denominator will be all children enrolled in the AMR sub-study whose stool was submitted for antimicrobial sensitivity testing (irrespective of whether the bacteria was isolated). Those children who were enrolled in the AMR study, who provided a sample, but whose sample could not be subject to an antibiotic sensitivity test because of external circumstances (COVID-19 related lockdowns of the lab), will be excluded from the denominator. At sites, that have experienced a lockdown, random distribution of selection of specimens for testing will be difficult to confirm, though examination for systematic bias (eg by date range) will be undertaken. If bias is suggested in sites that have not completed testing, these sites will be excluded from hypothesis testing. But other remaining sites will be included in non-inferiority test as outlined above.

In secondary analysis, the prevalence denominator will be defined as those children in whom the respective bacteria was isolated and tested (i.e. azithromycin resistance in *E. coli* as a proportion of *E. coli* isolates, and likewise for *S. pneumoniae*). Sites that have not completed testing as outlined above, will be dealt with as outlined above.

9.5.3. Exploratory analyses

For both the primary and secondary analyses, estimates of AMR prevalence will be adjusted for site and other potentially confounding covariates (including those listed in Section 4.5, and data on recent antibiotic use). Resistance analyses will be reported separately for Asia and African sites.

Change in resistance over time within individual participating children will be estimated using mixed effects models or by including baseline MIC in the model. If MICs will be reported as ordered categories then ordinal mixed effects models will be used. If reported categorically as Resistant/Sensitive then binomial mixed effects models will be used.

We will also describe the resistance prevalence in *E.coli* at baseline for both trial arms.

If azithromycin resistance is detected among participants' samples tested, then a separate exploratory analysis on resistance to one or more β -lactam antibiotics will be done.

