Data suggest that 80-90% of all children with diarrhoea currently receive antibiotics, despite WHO guidelines restricting antibiotics to a small subset with dysentery or cholera. The use of targeted empiric antibiotics for a small subgroup of severely ill children at high risk of death may also potentially lower antimicrobial resistance if such children defer to the use of more appropriate antibiotics than are commonly used in practice now (despite WHO guidelines) and if other children are less likely to use antibiotics based on an assessment of their being at lower risk. In addition, data from trials of antibiotics in acute respiratory illness also suggest that when clear guidelines are provided for the use of antibiotics in high risk children, antibiotic use decreases and resistance among isolated pathogens is reduced (10, 11).

After discussions with antimicrobial resistance experts at WHO and externally, we feel that careful documentation of the association between clinical failure and the development of resistance in the community during this trial would be useful to allow careful risk/benefit assessment of any proposed policy change if a mortality reduction benefit is shown. In a complementary linked study, we propose to study antimicrobial resistance to multiple antibiotics, among *Escherichia coli* and *Streptococcus pneumoniae* isolates in stool samples collected from a subgroup of participants at enrolment and in stool samples and naso-

pharyngeal swabs collected from the same subgroup of participants and their close household contacts at the 90-day and 180 days follow-ups. Additionally, we propose that stool be collected and stored at -80°C from all participants at enrolment for molecular detection of pathogens and identification of antimicrobial resistance genes at a later date. For the same purpose, we also propose to store stool and nasopharyngeal swab samples from the subgroup of participants at the 90-day and 180-day follow-ups.

Safety profile of azithromycin: A review of studies having used azithromycin in young children concluded that "...azithromycin given as a suspension once daily for 3 days is well tolerated and can be used safely for the treatment of acute bacterial infections in children of all ages. Even in very young children, there are no concerns regarding safety or tolerance." (13).

References

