2.3 Eligibility criteria

2.3.1 Inclusion criteria (all of):

- Children aged 2 – 23 months, presenting to a designated health care facility at a participating study site **WITH**
- Diarrhoea per caregiver perception **AND** at least 3 loose or watery stools in the previous 24 hours,
- Diarrhoea for less than 14 days prior to screening **AND** with at least one of the following criteria at presentation:
 - A. Signs of some or severe dehydration as per WHO Pocket Book 2013

- B. Moderately wasted as defined by a mid-upper arm circumference (MUAC) less than 125 mm (but greater than or equal to 115 mm) or a weight-for-length z-score (WLZ) greater than -3SD and less than or equal to -2SD after rehydration during stabilization period or
- C. Severely stunted (length-for-age z-score (LAZ) <-3 SD) **AND**
- Parent or guardian (caregiver) willing to allow household visits on DAY 2 and DAY 3 and willing to return to facility on DAY 90 **AND**
- Parent or guardian (caregiver) provides a consent for trial participation on behalf of the child, based on local standards

Exclusion criteria (any one of):

- Dysentery (gross blood in stool reported by caregiver or observed by healthcare worker [HCW]),
- Suspected *Vibrio cholerae* infection (determined according to WHO guidelines or clinical suspicion),
- Previously or currently enrolled in the ABCD study,
- Concurrently enrolled in another interventional clinical trial,
- Sibling or other child in the household enrolled in the ABCD study and currently taking study medication,
- Signs of associated infections (pneumonia, severe febrile illness, meningitis, mastoiditis or acute ear infection) requiring antibiotic treatment,
- Documented antibiotic use in the 14 days prior to screening (not including standard use of prophylactic antibiotics, i.e. co-trimoxazole use in HIV-exposed children),
- Documented use of metronidazole within the last 14-days,
- Known allergy or contraindication to azithromycin antibiotics,
- Severe acute malnutrition (SAM) defined as WLZ less than -3 SD, or MUAC less than 115 mm, or edema of both feet, OR
- Living too far from the enrolment health center to ensure adequate Directly Observed Therapy (DOT) on DAY 2 and DAY3

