9.6 Analysis of Outcome 8- Antibiotic resistance in contacts

To compare prevalence of azithromycin resistant *E. coli* and azithromycin resistant *S. pneumoniae* respectively in stool and nasopharyngeal swabs submitted for antimicrobial resistance testing at Day90 and Day180 among the siblings or close household contacts (children under five years of age living in the same household under the care of the same primary caregiver) of a random sub-sample of enrolled participants, by trial allocation arm. It should be noted that recruitment of the contacts themselves was non-random, biases by site and other factors are likely. Adjustments may be made using a modeling framework, but any arising results should be interpreted with caution and full caveats and limitations will be disclosed with any reporting of results. Such model adjusted outcomes will be described as exploratory.

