9.6.4 Exploratory analyses

For both the primary and secondary analyses, estimates of AMR prevalence will be adjusted for site and other potentially confounding covariates (including those listed in Section 4.5, and data on recent antibiotic use).

Resistance analyses will be reported separately for Asia and African sites.

Change in resistance over time within individual participating children will be estimated using mixed effects models or by including baseline MIC in the model. If MICs will be reported as ordered categories then ordinal mixed effects models will be used. If reported categorically as Resistant/Sensitive then binomial mixed effects models will be used.

If azithromycin resistance is detected among participants' samples or isolates tested, then a separate exploratory analysis on resistance to one or more B-lactam antibiotics in contacts will be done.

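### The exploratory resistance models adjust the arm comparison for recent antibiotic use, which most likely occurs after randomization and so cannot be a confounder

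*SAP*

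**What the plan says.** SAP 9.5.3 is headed "9.5.3. Exploratory analyses". It covers enrolled children in the antimicrobial resistance (AMR) sub-study and says that, under both denominators (all samples submitted, and isolates only), prevalence estimates will be "adjusted for site and other potentially confounding covariates (including those listed in Section 4.5, and data on recent antibiotic use"). SAP 9.6.4 repeats the plan for household contacts: "For both the primary and secondary analyses, estimates of AMR prevalence will be adjusted for site and other potentially confounding covariates", with the same list. Neither section says when the antibiotic use is measured, over what period, or on which form.

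The covariates in SAP 4.5 are age, sex, reason for enrolment and wealth quintile. The formal tests are in SAP 9.5.2 and 9.6.2. They are one-sided, use a 10-point margin and the continuity-corrected chi-square test of Dunnett and Gent, and name no covariates. For contacts, SAP 9.6 adds: "Such model adjusted outcomes will be described as exploratory".

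Protocol 2.3 lists among the exclusions: "Documented antibiotic use in the 14 days prior to screening", with prophylactic use exempt.

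**The concern.** A confounder must be able to influence which arm a child is in. Randomization rules that out for anything that happens afterwards. The SAP 4.5 covariates are characteristics that treatment cannot change. Antibiotic use in the weeks before a day-90 or day-180 sample is different, because allocation can change it: if azithromycin alters later illness, it alters later prescribing. Later use also shares causes with resistance, such as illness and care-seeking.

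A model that conditions on it no longer estimates the effect of allocation on resistance. It estimates something closer to the effect with other antibiotic use held fixed, and it can add bias through the shared causes. Labelling the variable a confounder invites readers to treat the adjusted figure as the cleaner one, when the reverse is true.

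**Working it through.** **1. When does the use occur?** The SAP does not say, so this is an inference from the following.
- Participants: the arm comparison uses day-90 and day-180 samples (SAP 9.5.1). Documented use in the 14 days before screening excludes a child (Protocol 2.3). Baseline variation is therefore limited to undocumented use, prophylaxis, or use more than 14 days before screening. None of these is naturally called recent relative to a day-90 sample.
- Contacts: no sample is taken before day 90 (Protocol 6.5). Use that is recent to a contact's sample follows the index child's randomization.
- Data source: Protocol 6.1 to 6.3 do not name antibiotic use among the items collected at day 45, 90 or 180.

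**2. The plan's own figure.** Protocol 10.3 gives 119 isolates per arm for 20% against 40%, 90% power and alpha 0.05. Two-sided and without continuity correction:

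n = [1.960 × √(2 × 0.30 × 0.70) + 1.2816 × √(0.20 × 0.80 + 0.40 × 0.60)]² / 0.20² = 108.2, that is 109.

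Continuity correction gives 119, so the figure reproduces. Nothing in this point changes it.

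**3. What the adjustment does.** Let d be the direct effect of azithromycin on resistance, g the effect of later antibiotic use on resistance, and Δq the difference in use (azithromycin minus placebo). Let U be an unmeasured cause of both use and resistance that adds u to resistance. In a linear model:
- Total (randomized) difference: T = d + g × Δq
- Difference adjusted for use: A = d − δ × Δq, where δ = u × cov(U, use | arm) / var(use | arm)
- Shift: A − T = −(g + δ) × Δq, which is zero when Δq = 0

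All inputs are assumed, since the documents give none. d is 10 points. Δq runs from 0 to −10 points. g runs from 0 to 20 points and u from 0 to 20 points. U is present in half of the children and raises use by 30 points, from 30% to 60% on placebo (mean 45%).

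| Case | T | A | Shift |
|---|---|---|---|
| Δq = 0, any g and u | 10.0 | 10.0 | 0 |
| Δq = −5, g = 10, u = 0 | 10 − 0.10 × 5 = 9.5 | 10.0 | 0.5 |
| Δq = −10, g = 20, u = 20 | 10 − 0.20 × 10 = 8.0 | 10 + 0.0632 × 10 = 10.6 | 2.6 |

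In the last row cov = 0.30 × 0.25 = 0.075. The variance is the mean of 0.45 × 0.55 and 0.35 × 0.65, which is 0.2375. So δ = 0.20 × 0.075 / 0.2375 = 0.0632. The sign of the shift reverses if use is higher on azithromycin.

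**4. Does a straddle of 10 points reverse the conclusion?** Protocol 10.3 expects about 1000 children in Africa and 750 in Asia, so about 1750 / 2 = 875 per arm with no losses. Take an observed difference of 8 points and the protocol's assumed placebo prevalence of 15% to 20%. SAP 9.5.2 states no one-sided alpha, so 5% is assumed. The upper limits are:
- 15% against 23%: 8 + 1.645 × √[(0.15 × 0.85 + 0.23 × 0.77) / 875] = 8 + 3.1 = 11.1 points
- 20% against 28%: 8 + 1.645 × √[(0.20 × 0.80 + 0.28 × 0.72) / 875] = 8 + 3.3 = 11.3 points

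Both exceed 10, so an unadjusted difference of 8 would not show non-inferiority either. Losses, continuity correction or a stricter alpha widen the limits further.

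**The case against.** The strongest reply is that nothing decisive depends on this sentence. It sits under an exploratory heading, the formal tests carry no covariates, and the SAP does not say that an adjusted difference will be read against the margin. All of that stands. A reader might infer that the main resistance comparison is biased, or that adjustment would reverse the non-inferiority conclusion. The documents support neither, and step 4 shows that point estimates on either side of 10 need not give different conclusions.

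The timing is inferred, and a baseline history is not ruled out. That also stands, though the sampling schedule makes it the less natural reading.

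A reader might also take the protocol's Background as showing that the arms will differ in other antibiotic use. It says "Data suggest that 80-90% of all children with diarrhoea currently receive antibiotics" and that targeted use "may also potentially lower antimicrobial resistance if such children defer to the use of more appropriate antibiotics than are commonly used in practice now". That passage is about prescribing under a targeted-use approach, not about the arms of this trial. Caregivers, site staff and hospital clinicians are blinded (Protocol 5.2), so later use could differ mainly through differences in illness. Nor do the documents support the inference that non-study antibiotics dilute the mortality and growth contrasts: they do not show that such data are held for the whole trial.

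Finally, contacts were not recruited at random and testing was interrupted by lockdowns, so a model with antibiotic use may have a place as a sensitivity check. That is fair, provided it is labelled as one.

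The exploratory label does not settle the matter. The sentence says that estimates for both the primary and the secondary analyses will be adjusted, which is ambiguous. SAP 4.3 requires country adjustment in all primary and secondary analyses, but the named test has no country term. The 9.5.3 model is thus where a site-adjusted arm estimate would come from, and there it is tied to a variable that probably follows randomization.

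**Conclusion.** The point holds for the exploratory adjusted estimates in SAP 9.5.3 and 9.6.4 and goes no further. Recent antibiotic use, as the SAP most likely means it, is not a confounder of the randomized comparison. Conditioning on it changes the estimand and can bias the adjusted arm difference. A shift needs two things: use must differ by arm, and use must either affect resistance or share causes with it. The documents give no data on either, so the size is unknown. The range of 0 to about 2.6 points rests wholly on the assumed inputs above. The formal tests, the sample size and the power are unaffected. This is a cheap improvement to the plan, not a threat to its main resistance result.

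**What to change.** In SAP 9.5.3 and 9.6.4, adjust the between-arm estimates only for country and pre-randomization covariates, and remove antibiotic use after randomization from the adjustment set. If a model with later antibiotic use is kept, for instance because of how contacts were recruited, state the window and the form the data come from. Label it a descriptive or mediation sensitivity analysis, and say that it is not read against the 10-point margin. Where the AMR sub-study holds the data, later non-study antibiotic use may also be tabulated by arm; this is optional.

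The cost is a sentence or two in two sections and slightly less precision in an exploratory model. No sample size, alpha or power figure changes.
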